Because of the possibility of drop-outs and other missed visits, there will be some missing data. The missing data complicate the planned statistical analyses for the specific aims, described above. With respect to the first specific aim, all available data will be included in calculating the correlation coefficients. For data that are missing, values can be imputed to generate the most extreme cases and the correlation coefficients can be determined under these circumstances. This approach will yield lower and upper boundaries for the estimated correlation coefficients and their confidence limits. In addition, a multiple imputation procedure will be implemented in order to account for the variability that occurs when replacing missing data with imputed values.

With respect to the second specific aim, the statistical analyses in the presence of drop-outs and missed visits is more complex, especially for the bivariate logistic regression analysis with generalized estimating equations (GEE). GEE requires that any missing data satisfy the assumption of "missing completely at random" (MCAR), i.e., the probability of response is independent of the observed and unobserved data (76). The MCAR assumption will be investigated and if it appears that it is violated, then likelihood-based regression models will be

implemented that assume either that the data are “missing at random” (MAR) or are non-ignorable (76).

G. Interim Analyses

The CLIC trial is not a typical effectiveness trial comparing treatments, so formal statistical analyses to evaluate effectiveness at interim time points will not be scheduled. However, an interim statistical analysis to evaluate the safety of the ICS and the LTRA will be scheduled at the midpoint of the trial and the results presented to the Data and Safety Monitoring Board (DSMB). The DSMB also will receive any reports of serious adverse events as they occur throughout the course of the trial.

H. Sample Size Justification

The target sample size for this trial is $N = 140$, and the justification is as follows. With respect to **Research Aim 1**, to test the null hypothesis that the Kendall correlation coefficient is zero versus a specified alternative at significance level α and statistical power $1 - \beta$, the approximate sample size formula is

$$N = 4(z_{1-\alpha/2} + z_{1-\beta})^2 / 9\tau^2$$

where $z_{1-\alpha/2}$ and $z_{1-\beta}$ represent appropriate percentiles from the standard normal distribution (77). For a two-sided, 5% significance level test with 90% statistical power ($\alpha = 0.05$ and $\beta = 0.10$) against the alternative that $\tau = 0.2$, the required sample size is $N = 117$. However, to account for a maximum of 15% drop-outs and/or missed visits, it is necessary to increase the sample size to $N = 140$.

With respect to the exploratory statistical analyses planned for **Research Aims 2 and 3**, the sample size of 140 is in effect. The target sample size of $N = 140$ is chosen because it provides a 95% confidence interval with endpoints ± 0.15 for a Pearson-type correlation when the true correlation is 0.5 or greater and there is a maximum of a 15% drop-out rate. Although logistic regression analyses will be applied in addition to linear regression analyses (which yield Pearson-type correlations), the estimated parameter coefficients from a maximum likelihood algorithm in a logistic regression model will behave in a similar manner.

A sample size of $N = 210$ would provide a tighter 95% confidence interval than with $N = 140$, with endpoints ± 0.10 for a Pearson-type correlation when the true correlation is 0.5 or greater. Therefore, it may be desirable to recruit this larger number of subjects, if possible.

Recruitment will be monitored to determine whether it is feasible to pursue this larger sample size.

XII. Significance

The primary significance of the CLIC study is to evaluate the response relationship of inhaled fluticasone propionate and oral montelukast in a patient population of children with mild to moderate persistent asthma. The results of this protocol will allow us to determine whether the response to one medication is independent of response to the other among patients. This will provide the core information necessary to describe variability in response and allow association of response to asthma phenotype and the presence of relevant genetic features. This is the first study designed to evaluate response to two medications and relate the response to asthma phenotype and well-described genetic markers of disease modification and potential medication response. Studies of this nature have not been performed in asthmatic children. We also explore the associated relationship of measurements of pulmonary function with forced oscillation, as compared to spirometry in measuring response to these medications and symptom control. This will provide valuable information for the application of these additional measures on pulmonary function with long term control therapy. This could provide insight into the application of these pulmonary function measures in asthma patients, especially young children, who are not able to perform full forced expiratory flow maneuvers.

There are several distinct advantages to pursuing the areas of research encompassed by CLIC. First, the response to the two medications in children with persistent asthma will be described. Second, the results may permit the identification of patients who fail to respond to one medication but respond to the other medication. Third, the evaluation of the asthma phenotype may lead to the description of asthma characteristics that are associated with a favorable response or lack of response to each of the medications. Finally, the association of an asthma phenotype with the type of response, could lead to identification of genetic markers that would be useful in genetic screening prior to medication selection (78). This type of assessment recently has been reported in response to chemotherapy for glioma (79, 80). If the latter observation is feasible for asthma therapy, then additional studies will be developed in the CARE Network to obtain confirmatory data on the relation of the genetic marker to response, and to evaluate the reproducibility of medication response in patients described as responders and nonresponders. An additional study could also evaluate other response markers, such as reduction in airway hyperresponsiveness and reduction in symptoms, to name a few. Studies could also be developed to assess the presence of a certain genotype to predicted response to a medication.

References

1. National Asthma Education and Prevention Program Expert Panel Report 2: Guidelines for the Diagnosis and Management of Asthma. National Institutes of Health, National Heart, Lung, and Blood Institute, Publ. No. 97-4051, 1997.
2. Dunhill MS. The pathology of asthma with special reference to changes in the bronchial mucosa. *J Clin Pathol* 1960;13:27-33.

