 - f. Urine pregnancy test for female patients who have reached menarche
 - g. Participation concludes and recommendations given for further care, including prescription for open label controller medications.

9. Week 18 Visit 7
 - a. Subject returns two weeks after Visit 6
 - b. Visit to assess asthma control and any adverse drug reactions
 - c. Spirometry
 - d. Return diary and electronic peak flow meter

IV. Inclusion and Exclusion Criteria

A. Inclusion Criteria

1. Male and female patients 6 to <18 years of age at enrollment.

2. Able to perform reproducible spirometry and demonstrate one or both of the following: reversible airflow obstruction ($\geq 12\%$ improvement in FEV₁ following the maximal bronchodilator testing procedure with albuterol MDI) or a methacholine PC₂₀ ≤ 12.5 mg/ml.
3. History of clinical varicella or varicella vaccine.
4. Combination of asthma symptoms or rescue bronchodilator use on an average of 3 or more days per week during the last 4 weeks.
5. Nonsmoker in the past year. In addition, no use of smokeless tobacco products in the past year.
6. Ability of parent to provide informed consent, as evidenced by signing a copy of the consent form approved by the Institutional Review Board of the subject's respective study institution.
7. Verbal assent for children less than 7 years of age and written assent for those between 7 and 18 years of age.

B. Exclusion Criteria

1. Corticosteroid treatment for any condition within the defined intervals prior to enrollment (route)
 - a. Oral - None within 4 weeks prior to Visit 1.
 - b. Oral Inhaled - None within 4 weeks prior to Visit 1. Nasal steroids may be used during the trial provided it is continuous maintenance therapy.
 - c. Injectable – None within 4 weeks prior to Visit 1.
2. Current or prior use (within the previous 4 weeks of Visit 1) of medications known to significantly interact with corticosteroid disposition, including but not limited to carbamazepine, erythromycin or other macrolide antibiotic, phenobarbital, phenytoin, rifampin, ketoconazole, and sibutramine (Meridia).
3. Symptoms during the assessment/characterization period (between Visits 1 and 2) such that
 - a. The subject has symptoms requiring albuterol use more than four times (8 inhalations) per day on average, excluding pre-exercise albuterol use.
 - b. The subject has nighttime awakenings from asthma two or more times per week on average.

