Adverse events due to concurrent illnesses other than asthma may be grounds for withdrawal if the illness is considered significant by the study investigator or if the patient is no longer able to effectively participate in the study. Subjects experiencing minor intercurrent illnesses may continue in the study provided that the nature, severity, and duration of the illness are recorded and that any unscheduled medications required to treat the illness are also recorded. Examples of minor intercurrent illnesses include acute rhinitis, sinusitis, upper respiratory infections, urinary tract infections, and gastroenteritis. Medications are allowed for treatment of these conditions in accordance with the judgment of the responsible study physician.

Documentation of an adverse event unrelated to asthma will be recorded on an Adverse Event Report Form and will include the following information:

1. Description of the illness
2. Dates of illness
3. Treatment of illness and dates (medications, doses, and dose frequency)
4. Whether emergency treatment or hospitalization was required
5. Treatment outcome

C. Adverse Events Related to Asthma Exacerbations

Definition - for this protocol, an asthma exacerbation is defined as the development of an increase in symptoms of cough, chest tightness, and wheezing in association with one or more of the following:

- An increase in "as needed" or rescue albuterol use of ≥ 8 inhalations over a 24-hour period above baseline use (baseline defined as average daily use during the period from Visit 1 to randomization at Visit 2), or ≥ 16 total inhalations over a 24-hour period.

- A fall in PEF of $\leq 65\%$ from personal best (personal best is defined as the best of 3 acceptable post-bronchodilator blows on the peak flow meter performed at Visits 1 and 2) or $FEV_1 \leq 80\%$ of baseline

Patients developing asthma exacerbations during the double-blind treatment period and during the off-treatment period will be managed according to the following rescue algorithms. Patients developing asthma exacerbations during the assessment/characterization period will be removed from the study. Once the exacerbation has been resolved the patient may be considered for re-enrollment, starting again with Visit 1.

1. Rescue Algorithms

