Rescue algorithms will be applied in cases where an exacerbation as defined in Section C fails to resolve or PEF is not improved to $> 65\%$ of personal best within 24 hours after increasing PRN albuterol use. Rescue algorithms are based on recommendations from the NAEP Guidelines for Diagnosis and Management of Asthma (NHLBI Publication No. 97-4051, 1997). Albuterol and oral prednisone are the principal medications for rescue management and patients will be instructed in their use for home management. For severe acute episodes of asthma, treatment will be administered according to the best medical judgment of the treating physician and additional medications will be used as determined by clinical judgment.

2. Home Care

Asthma exacerbations will be recognized by an increase in symptoms and/or a drop in PEF below personal best. Patients will be educated to recognize exacerbations as early as possible to facilitate prompt treatment and to lessen morbidity.

- Patients who recognize increased symptoms and/or a fall in PEF $\leq 65\%$ of personal best will use albuterol by MDI, 2-4 puffs, every 20 min up to 60-90 min if needed and then every 4 hours, or less, if needed. Patients will be instructed to use the “PRN MDI” for treatment.
- If the PEF does not increase to $> 65\%$ of personal best or if symptoms are not improved after the first 60-90 min of therapy, the patient should contact the investigator, their primary physician or seek care in the emergency department.

- Failure of albuterol to control or maintain PEFR > 65% of personal best should indicate the use of corticosteroids (see below).

a. Physician's Office or Emergency Room Treatment

- Patients will be assessed by history, physical examination, and by physiological monitoring including spirometry or PEFR. If the patient's PEFR or FEV₁ are less than 25% predicted or if the patient shows evidence of altered mental status, cyanosis, labored breathing, or use of accessory muscles, sampling of arterial blood for respiratory gas analysis is indicated with appropriate action taken depending on the results obtained.
- When treated in the physician's office or the hospital emergency room, patients should initially be given albuterol by nebulization (0.5 cc of 0.5% solution) every 20 min over the first 60-90 min.

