- If the PEFR increases to > 65% of personal best after the first 60-90 min, the patient can be discharged to continue treatment at home. Prednisone may be administered at the discretion of the physician to augment therapy (see C.2.b).
- If symptoms persist and PEFR remains ≤ 65% of personal best, nebulized albuterol should be continued as often as every hour and further treatment with oral or parenteral corticosteroids should be considered (2 mg/kg or maximal 60 mg prednisone orally; methylprednisolone 2 mg/kg or maximal 60 mg iv bolus). Monitoring of PEFR or spirometry should continue every hour. Within 4 hours of treatment, a decision should be made regarding patient disposition.
- If PEFR increases to > 65% of personal best within 4 hours, the patient can be discharged to continue treatment at home. Home treatment should include a 4-day course of prednisone (see below).
- If PEFR remains > 40% but ≤ 65% of personal best, an individualized decision should be made to hospitalize the patient for more aggressive therapy or to continue therapy at home with a course of prednisone.
- If PEFR is ≤ 40% personal best after repeated albuterol treatments, the patient should be admitted to the hospital unless in the physician's best judgment alternative treatment could suffice.

b. Prednisone Treatment

In this protocol, prednisone will be used when acute exacerbations cannot be controlled by albuterol therapy. Indications for prednisone therapy include the following:

- For follow-up management after discharge from the physician's office, emergency room, or hospital for an acute exacerbation.
- For home management if the patient is taking ≥ 8 inhalations over a 24-hour period above baseline use or ≥ 16 puffs albuterol over a 24-hour period and despite this therapy, PEFr remains $\leq 65\%$ personal best before albuterol use.

The dose of prednisone used during an acute exacerbation shall consist of 2 mg/kg per day or 60 mg maximum as a single dose every day for 2 days, followed by 1 mg/kg per day, or a 30 mg maximum as a single dose every day for 2 more days. The decision to initiate or to continue a course of prednisone beyond 4 days is left to the discretion of the physician.

D. Study Center Visits Following Exacerbations

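### Protocol VII.C words the PEF exacerbation criterion as a size of fall (at most 65%) where the rest of the section uses a level (at or below 65% of personal best)

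*Protocol*

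**What the plan says.** Protocol Section VII.C requires an increase in symptoms together with one or more objective criteria. The first bullet concerns rescue albuterol use. The second gives a PEF criterion, "A fall in PEF of $\leq 65\%$ from personal best", and an FEV₁ criterion, which is a level (at or below 80% of baseline). Personal best is the "best of 3 acceptable post-bronchodilator blows on the peak flow meter performed at Visits 1 and 2".

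The definition is used in two places:

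- **Before randomization (VII.C):** "Patients developing asthma exacerbations during the assessment/characterization period will be removed from the study". The next sentence adds: "Once the exacerbation has been resolved the patient may be considered for re-enrollment, starting again with Visit 1".
- **During treatment (VII.C.1, Rescue Algorithms):** rescue applies where "an exacerbation as defined in Section C fails to resolve" or, as a separate alternative, where "PEF is not improved to $> 65\%$ of personal best within 24 hours" of increased albuterol use.

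The treatment rules that follow state 65% as a level of personal best. For home prednisone in VII.C.2.b, for example, one condition is that "PEFr remains $\leq 65\%$ personal best before albuterol use".

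**The concern.** A fall of a given percentage from a reference is the size of the drop, not the value reached. A drop of at most 65% takes in trivial dips and leaves out the deepest falls, which is the wrong way round for a criterion of worsening asthma. It also conflicts with the 65% level in the rescue and prednisone rules.

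At the mild end, a child with increased symptoms and a 10% dip in PEF during the assessment period would count as having an exacerbation and would have to be removed. At the severe end, a child below 35% of best would not meet this criterion, although the albuterol or FEV₁ criterion might still apply.

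The PEF criterion carries extra weight between Visits 1 and 2. The albuterol criterion relative to baseline uses average use over that whole interval, which is not complete until Visit 2. Section XI.D takes baseline FEV₁ at Visit 2; VII.C does not define it separately. If that baseline applies, the criteria usable during the interval are 16 or more total inhalations in 24 hours and PEF against the personal best determined at Visit 1.

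**Working it through.** No sample size or error rate is involved, so there is no plan figure to reproduce. The check sets the literal criterion against the level used later in the section.

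**Definitions.** Let p be PEF as a percentage of personal best, and let the fall be d = 100 − p.

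- Literal (VII.C): 0 < d ≤ 65, which gives 35 ≤ p < 100.
- Level (VII.C.1, VII.C.2): p ≤ 65, which is d ≥ 35.

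**Comparison, with an illustrative personal best of 300 L/min:**

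| PEF (L/min) | p | d | Literal met | Level met |
|---|---|---|---|---|
| 270 | 90% | 10% | yes | no |
| 198 | 66% | 34% | yes | no |
| 195 | 65% | 35% | yes | yes |
| 105 | 35% | 65% | yes | yes |
| 90 | 30% | 70% | no | yes |

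The bounds are 0.35 × 300 = 105 and 0.65 × 300 = 195. The two rules agree that the criterion is met only for p from 35% to 65%. Between 65% and 100% only the literal rule is met; below 35% only the level is.

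**Could the inequality sign simply be reversed?** A fall of at least 65% gives p ≤ 35%, which does not match the later rules either. The fault is in the words of the phrase, not the sign.

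**How easily is the literal criterion met?** Personal best is measured after bronchodilator, so a reading before albuterol can lie below it without any worsening. If PEF rises by a proportion r after albuterol, the pre-albuterol reading is 1/(1 + r) of best. Inclusion criterion 2 in IV.A offers, as one of two routes, an FEV₁ improvement of at least 12% "following the maximal bronchodilator testing procedure with albuterol MDI". The protocol gives no PEF reversibility, so the 12% line assumes PEF reverses in the same proportion as FEV₁, and 5% to 25% is an assumed range:

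- r = 0.05: 1/1.05 = 95.2% of best, a 4.8% fall
- r = 0.12: 1/1.12 = 89.3% of best, a 10.7% fall
- r = 0.25: 1/1.25 = 80.0% of best, a 20.0% fall

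Each meets the literal criterion and none meets the level. For such a child, increased symptoms alone would decide.

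**The case against.** The strongest reply is that nobody would be misled. VII.C.1 and VII.C.2 use 65% of best as a level for rescue, home albuterol, discharge and prednisone, the FEV₁ half of the same bullet is a level, and the literal reading is clinically absurd. Section IV.B also sets separate exclusions for the assessment period, including PEF variability of 30% or more, which implies that children with smaller swings are meant to stay in. That period lasts only 5 to 10 days, and re-enrollment is possible.

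Nor is there much of a safety gap. Home Care starts albuterol on symptoms alone, the second rescue alternative catches PEF that has not recovered above 65% of best, and admission is tied to 40% of best or less after repeated albuterol. Finally, the reversibility illustration rests on an assumption about PEF, and 12% reversibility is only one of two entry routes.

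Most of this stands, and it is why the point is minor. It does not make the sentence correct. The removal rule has no correctly worded threshold of its own; it relies on the definition. The opening sentence of Home Care, which describes recognizing an exacerbation by a drop below personal best without giving a level, would not correct a coordinator who applied VII.C literally. The wording finding does not depend on the reversibility illustration.

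**Conclusion.** The concern holds, as a minor wording error in an operative threshold. As written, the PEF criterion is met from 35% to just under 100% of personal best and missed below 35%. The rest of the section supports a criterion met at 65% of best or less. The arithmetic needs no assumption beyond reading the phrase literally.

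The consequences are limited to possible unnecessary removal before randomization and an ill-defined first rescue alternative. The protocol gives no data on how many children would be affected. Treatment failure (IV.C) and drop-out (XI.E) do not use this criterion, and no effect on the primary outcome, the sample size or the analysis is claimed.

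**What to change.** In Section VII.C, replace the PEF criterion with: a fall in PEF to ≤65% of personal best. Apply that same criterion when deciding removal in the assessment period. In Home Care (VII.C.2), inserting 'to' before the 65% figure in the first bullet would be optional copy-editing, since that sentence already reads as a level.

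The cost is one phrase, using a value already in the protocol. Procedures, sample size and analysis are unchanged.
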